Title: Minimization of Bleeding Related Adverse Drug Events in Plastic & Reconstructive Surgery

NCT03212365

Document date: 8.6.2020

Study Protocol

Patients

Eligible patients were 18 years of age or older, had a planned definitive plastic and reconstructive surgery operation under a general anesthetic, and had planned post-operative admission of at least two overnights. All patients had sequential compression devices placed in the OR and continued during inpatient admission. Patients were ineligible if they had any one of the following: contraindication to use of enoxaparin, intracranial bleeding or stroke, hematologic or bleeding disorder, known heparin-induced thrombocytopenia, creatinine clearance ≤ 30 mL/min, serum creatinine > 1.6 mg/dL, epidural anesthesia, or patient/surgeon desire to be provided with non-enoxaparin chemical prophylaxis after surgery. Patients who received peri-operative aspirin were eligible for the study. Patients whose gross weight was > 150 kg were excluded. There was no minimum study weight. All patients provided written informed consent prior to their planned definitive operation.

Study Procedures

Patients were randomized immediately after their planned definitive operation, following a direct conversation between the Principal Investigator ([name]), primary plastic surgeon, and consultant surgeons or physicians. Primary surgeons had the discretion to decline study participation based on intra-operative events, such as procedure less invasive than planned or concern for intra-operative bleeding. Eligible patients were randomized to enoxaparin 40mg twice daily or enoxaparin 0.5mg/kg twice daily.

Investigational Pharmacy randomized patients and then provided study drug in identical syringes containing clear liquid; all doses were diluted to 1.0cc volume. Patients received the

first dose of study drug as a subcutaneous injection between 7 and 8 hours after the procedure ended, and every 12 hours thereafter until discharge from the hospital.

Patients had peak and steady state aFXa levels drawn after the third enoxaparin dose, at steady state. Goal peak steady state aFXa was 0.2-0.4 IU/mL. Investigational Pharmacy identified patients with out-of-range peak aFXa levels and performed real time enoxaparin dose adjustment. Dose adjustment was performed because initial low aFXa levels have significantly increased risk of VTE and high aFXa levels have been associated with bleeding. Therefore, not providing real time dose adjustment in response to documented aFXa levels would have been ethically marginal. Patients whose level was in-range continued on their initial enoxaparin dose until discharge. Patients who received real time dose adjustment underwent dose optimization until in-range peak aFXa level was achieved, and then received that dose until discharge.

Patients did not routinely receive post-discharge enoxaparin prophylaxis; this was provided only at attending physician discretion. When applicable, the resident physician received unblinded dose information, allowing the attending physician to remain blinded and objectively identify secondary outcome events while providing patients with a pharmacokinetically optimized dose.

The primary outcome (aFXa level in response to initial enoxaparin dose) occurred 36 hours after surgery, and could not be confounded by dose adjustment or receipt of post-discharge enoxaparin.

Patients received standard post-operative care from the primary surgeon. The study team contacted all randomized patients at 90 days to identify secondary outcomes.

Study Outcomes

Study outcomes were defined prior to enrollment of Patient #1, and definitions were published previously (Pannucci et al, “Double-Blind Randomized Clinical Trial to Examine the Pharmacokinetic and Clinical Impacts of Fixed Dose versus Weight-based Enoxaparin Prophylaxis: A Methodologic Description of the Fixed or Variable Enoxaparin (FIVE) Trial”, PubMed ID 31321183).

Both primary outcomes were pharmacokinetic outcomes derived from the initial peak steady state aFXa level, drawn at 36 hours after conclusion of the operation. The initial peak steady state level was in response to the initial enoxaparin dose; when dose adjustment was required, this level was not considered in the primary outcome. The primary effectiveness outcome was avoidance of under-anticoagulation (peak aFXa <0.20 IU/mL). The primary safety outcome was avoidance of over-anticoagulation (peak aFXa >0.40 IU/mL). Post dose-adjustment aFXa levels, if drawn, were not considered in the primary outcomes. Both secondary outcomes were obtained at 90 days after surgery. The secondary effectiveness outcome was 90-day symptomatic VTE, and the secondary safety outcome was 90-day clinically relevant bleeding.

Symptomatic VTE was defined as 1) any imaging-confirmed deep venous thrombosis (DVT) event, including upper limb, lower limb, or central, 2) any imaging-confirmed pulmonary embolus event, 3) any autopsy-proven VTE, and/or 4) 90-day mortality in which VTE could not be excluded (eg PEA arrest without autopsy). Patients were not screened for VTE events unless symptoms were present.

Major bleeding was defined using the published consensus definition of major bleeding for randomized controlled trials that examine anti-hemostatic drugs from the International Society of Thrombosis and Hemostasis. Major bleeding included any of the following events: bleeding requiring two or more units of blood transfusion, bleeding requiring bedside hematoma

evacuation or interventional radiology procedure, bleeding requiring unplanned return to the operating room, bleeding into a critical anatomic space, or fatal bleeding. In addition, we tracked clinically relevant bleeding, which was defined more broadly to include bleeding which required enoxaparin cessation in addition to all major bleeding factors.

90-day bleeding and VTE were compared between groups using a survival analysis log-rank test.

Outcome events were blindly adjudicated.

Statistical Analysis

The FIVE trial's sample size calculations and justifications were previously published (Pannucci et al, "Double-Blind Randomized Clinical Trial to Examine the Pharmacokinetic and Clinical Impacts of Fixed Dose versus Weight-based Enoxaparin Prophylaxis: A Methodologic Description of the Fixed or Variable Enoxaparin (FIVE) Trial", PubMed ID 31321183).

Statistical analyses were performed using Stata15 (StataCorp; College Station, Texas).

We compared patient-level variables (Tables 1 and 2) between groups using student's t-test for continuous variables, chi-square or Fisher's exact test for dichotomous variables, and Wilcoxon rank-sum test for ordinal variables.

The primary effectiveness outcome was avoidance of under-anticoagulation (peak aFXa <0.20 IU/mL). Initial sample size estimates for under-anticoagulation avoidance were obtained

from a prior clinical trial, which established that 90.4% of patients who received enoxaparin 40mg twice daily were not under-anticoagulated. We assumed the rate of not being under-anticoagulated was 90.4% in the weight-based group. The primary effectiveness analysis was a noninferiority analysis with a two-sided test at the 0.05 level. The noninferiority margin was set at -12%. To achieve 90% power using a two-sided comparison with alpha of 0.05, using a two-sided 95% confidence interval around the difference in proportions, 127 patients per group were needed. The noninferiority hypothesis was tested by a Poisson regression model for binary outcomes with robust standard errors. After the Poisson model was fit, marginal estimation was used to calculate the 95% confidence interval around the difference in proportions. This method took the two estimated proportions used in the risk ratio, subtracted them, and computed the confidence interval for non-inferiority testing. To obtain a two-sided noninferiority test p-value, we used a Wald post-test to compare the difference in proportions to the noninferiority margin constant -0.12.

The primary safety outcome was avoidance of over-anticoagulation (peak aFXa >0.40 IU/mL). Initial sample size estimates for over-anticoagulation were obtained from a prior clinical trial, which showed that 72.2% of patients who received enoxaparin 40mg twice daily were not over-anticoagulated. We assumed that weight-based dosing would increase the proportion of patients not over-anticoagulated to 90%. To detect this difference with 90% power using a two-sided comparison with alpha of 0.05, 100 patients per group were needed. For this outcome, a Poisson regression model for binary outcomes with robust standard errors was fitted.

The Data Safety and Monitoring Board reviewed unblinded 90-day VTE and bleeding data every six months. To avoid an increased risk for type I error, no interim analyses were performed on primary outcomes.

After 254 patients were randomized, the study statistician reviewed unblinded data to determine the number of patients who did not produce primary outcome data. No interim statistical analysis was performed at this phase, to avoid an increased risk for type I error. The planned sample size was adjusted upward to 295, to include at least 127 patients in each group who produced primary outcomes data.

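### Does naming only a log-rank test for 90-day bleeding and VTE leave the clinical comparison uninterpretable?

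*Combined protocol and SAP*

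**What the plan says.** Study Outcomes makes 90-day symptomatic VTE the secondary effectiveness outcome and states that "the secondary safety outcome was 90-day clinically relevant bleeding". The analysis of both is one sentence: "90-day bleeding and VTE were compared between groups using a survival analysis log-rank test". It gives no effect measure, interval, margin, expected rate or power for either.

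Statistical Analysis says more about the primary effectiveness outcome. A Poisson model is fitted, then "marginal estimation was used to calculate the 95% confidence interval around the difference in proportions", and the result is judged against a margin of -12 points. For the primary safety outcome it says only that a Poisson model with robust standard errors was fitted, and names no effect measure or interval.

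The sample sizes of 127 and 100 per group are both derived from aFXa proportions. The later increase had the same basis: "The planned sample size was adjusted upward to 295, to include at least 127 patients in each group who produced primary outcomes data". Study Procedures says that "high aFXa levels have been associated with bleeding" and describes dose adjustment after the first level: "Patients who received real time dose adjustment underwent dose optimization until in-range peak aFXa level was achieved, and then received that dose until discharge".

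**The concern.** A log-rank test gives a p-value and nothing else. The stated sample size was not set for bleeding or VTE, so a p-value above 0.05 would be unsurprising and would not show which clinical differences remain possible. Bleeding and VTE are the outcomes that matter most to patients, yet they have the thinnest specification. A reader could take a non-significant result as evidence that the two regimens are clinically alike. A reader could also overlook that the comparison is of a starting dose followed by aFXa-guided adjustment, not of two unadjusted doses.

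**Working it through.** **Inputs from Statistical Analysis.** For the fixed dose, "72.2% of patients who received enoxaparin 40mg twice daily were not over-anticoagulated". For the other arm, "We assumed that weight-based dosing would increase the proportion of patients not over-anticoagulated to 90" per cent. Over-anticoagulation is therefore 1 - 0.722 = 0.278 against 1 - 0.90 = 0.10, a gap of 0.178. Under-anticoagulation is planned at 1 - 0.904 = 0.096 in both arms. The total is 295 patients, taken as 147 fixed and 148 weight-based. The document does not state the allocation ratio; equal allocation is inferred from the equal per-group targets.

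**The plan's own figures.**

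- Safety: the pooled two-proportion formula for 72.2% v 90%, two-sided 0.05 and 90% power, gives 99.6, so 100 per group.
- Effectiveness: 2 × 0.904 × 0.096 × (1.960 + 1.282)² / 0.12² = 126.6, so 127 per group.

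Both stated figures reproduce, and neither involves a clinical event.

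**Bleeding power (illustrative).** Three things must be assumed, because the document gives no bleeding rate:

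- a 90-day risk r of 2% to 8% without over-anticoagulation;
- an excess D of 5 to 20 points with it;
- no other route by which the arms differ.

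Let k be the share of the excess left after dose adjustment. Arm risk = r + (share over-anticoagulated) × D × k, so the arm difference is 0.178 × D × k. With k = 1 this is 0.9 to 3.6 points.

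Example with r = 5%, D = 10 points, k = 1:

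- Fixed: 0.05 + 0.278 × 0.10 = 7.78%. Weight-based: 0.05 + 0.10 × 0.10 = 6.00%. Difference: 1.78 points.
- Pooled standard error: √(0.0689 × 0.9311 × (1/147 + 1/148)) = 2.95 points, so significance needs a difference of about 5.8 points.
- Power is about 9% (two-proportion formula 9.3%; simulated log-rank 8.7%).

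Simulated log-rank power (4,000 runs, two-sided 0.05):

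| r | k = 1; D = 5 / 10 / 20 points | k = 0.5; D = 5 / 10 / 20 points |
|---|---|---|
| 2% | 6.1 / 12.2 / 25.8% | 4.6 / 7.3 / 11.7% |
| 5% | 6.1 / 8.7 / 19.9% | 4.8 / 5.5 / 9.0% |
| 8% | 5.3 / 7.7 / 15.6% | 5.2 / 5.8 / 7.9% |

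**Sensitivity to the assumptions.** If the excess is expressed as a relative risk of 2 to 5 on a baseline of 2% to 10%, power reaches about 37%. With a relative risk of 10 it is about 52% at a 5% baseline and 88% at 10%. The aFXa rates do set one limit: if bleeding differs only through over-anticoagulation, the risk ratio between arms cannot exceed 0.278 / 0.10 = 2.78. They do not fix the power.

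**VTE.** With 9.6% under-anticoagulated in both arms, no difference is expected by that route. This is a planning assumption for the noninferiority calculation, not a forecast of VTE.

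**Precision.** For equal risks, the simple Wald half-width is 1.96 × √(p(1 - p)(1/147 + 1/148)): 3.2, 5.0 and 6.2 points at p = 2%, 5% and 8%. At small counts a score interval is preferable and wider. With 3, 7 and 12 events per arm (about 2%, 5% and 8%), its half-width is roughly 4.0, 5.3 and 6.5 points.

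**The case for a change.** The strongest case for a change is that a p-value with no interval or margin cannot support a statement of no difference, whatever the power. The plan gives a difference and an interval for one primary outcome and could do so here for a few lines of text and two table columns. The principle stands. So does the observation that the sample size was not set for these outcomes.

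Four points count against turning it into a change.

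- The document nowhere says that a non-significant secondary result means clinical equivalence, so the misreading would be the reader's own.
- The contrast with the primary analysis is selective. The effectiveness outcome has an interval because noninferiority is judged by one. The primary safety outcome has no interval named either, so silence in this short text does not show that only a p-value would be reported.
- Low power cannot be derived from the plan's aFXa rates alone. It needs the assumed bleeding rates above and a model in which only the 0.40 IU/mL threshold matters.
- The document refers to a published methods paper for its outcome definitions and sample size justification. That paper was not available for this check.

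**Conclusion.** No change to the plan is needed. The observation is correct: for 90-day bleeding and VTE the document names a test and no estimate. But the test is valid for the randomised comparison, no stated rule yields a wrong result, and the primary outcomes are unaffected. What is missing is ordinary reporting from the same event data: events and 90-day risk per arm, with a risk difference or hazard ratio and its interval. Competent analysts supply that without being told.

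The illustrated power of about 5% to 26% holds only under the assumed risks, with bleeding differing solely through over-anticoagulation. It is a reason to read the secondary results with care, as results of a starting dose plus aFXa-guided adjustment. It does not show an error in the plan.

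### Do two primary tests on opposite tails of one aFXa level, each at two-sided 0.05, need a rule linking them?

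*Combined protocol and SAP*

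**What the plan says.** Study Outcomes defines the pair: "Both primary outcomes were pharmacokinetic outcomes derived from the initial peak steady state aFXa level". Effectiveness is a peak that is not below 0.20 IU/mL; safety is a peak that is not above 0.40 IU/mL.

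Statistical Analysis treats them separately. On effectiveness: "The primary effectiveness analysis was a noninferiority analysis with a two-sided test at the 0.05 level", with a margin of −12% and 127 patients per group. On safety, where the proportion not over-anticoagulated is assumed to rise from 72.2% to 90%: "To detect this difference with 90% power using a two-sided comparison with alpha of 0.05, 100 patients per group were needed". The sentence on the safety analysis itself names only the model (Poisson with robust standard errors), so its alpha is taken from the sample-size sentence.

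The type I error statements concern interim looks: "To avoid an increased risk for type I error, no interim analyses were performed on primary outcomes". No section gives an order of testing, a both-must-win rule, an alpha split or a definition of overall trial success. Outcome definitions and sample-size justification are also referred to a methods publication, which was not available for this check.

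**The concern.** The two outcomes are opposite ends of one measurement. Lower exposure tends to reduce values above 0.40 and to raise the number below 0.20. Study Procedures treats both ends as harmful: "Dose adjustment was performed because initial low aFXa levels have significantly increased risk of VTE and high aFXa levels have been associated with bleeding". It also speaks of a single primary outcome: "The primary outcome (aFXa level in response to initial enoxaparin dose) occurred 36 hours after surgery".

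A reader could therefore worry about two things. First, two primary tests each use a full two-sided 0.05, although the plan takes care over type I error elsewhere. Second, a reduction in over-anticoagulation obtained by under-dosing would win the safety test and fail noninferiority, and the plan does not say how that pair of results is to be read. If the safety win were presented alone as the trial's success, the conclusion would mislead.

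**Working it through.** **Inputs (Statistical Analysis).** Not under-anticoagulated: 90.4% in both arms, so 9.6% under. Margin 12 points. Not over-anticoagulated: 72.2% fixed dose and 90% weight-based, so 27.8% and 10% over. The last paragraph of the section aims for at least 127 evaluable per group.

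**1. Stated sample sizes.**
- Noninferiority: n = (1.960 + 1.282)² × 2 × 0.904 × 0.096 / 0.12² = 126.6, so 127.
- Safety, mean proportion 0.811: n = [1.960 √(2 × 0.811 × 0.189) + 1.282 √(0.722 × 0.278 + 0.90 × 0.10)]² / 0.178² = 99.6, so 100.

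Both match, and both use the full two-sided 0.05 for their own test.

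**2. Joint behaviour at the planned rates.** Counts (under, in range, over) were enumerated exactly as trinomials with 127 per arm. Noninferiority used a Wald 95% interval against −12%; safety used the robust log risk ratio.

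| Result | Probability |
|---|---|
| Noninferiority met | 90.2% |
| Safety won | 96.0% |
| Both | 86.4% |
| Safety won, noninferiority not met | 9.6% |

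Noninferiority fails in 100 − 90.2 = 9.8% of trials, and 9.6 of those 9.8 points come with a safety win. The split result at the planned rates is thus the type II error already accepted when the noninferiority test was given 90% power.

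**3. False favourable results.** The worst case has both nulls true in the weight-based arm: 9.6 + 12 = 21.6% under and 27.8% over. Noninferiority is then falsely shown in 2.8% of trials, safety is falsely won in 2.4%, and at least one occurs in 5.2%.

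This case is hard to reach. For a lognormal level, the log-SD is ln(0.40/0.20) divided by the sum of the two normal quantiles:
- fixed dose: 0.693 / (1.305 + 0.589) = 0.37
- weight-based as planned: 0.693 / (1.305 + 1.282) = 0.27
- joint null: 0.693 / (0.786 + 0.589) = 0.50

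Weight-based dosing would have to widen the spread of levels, whereas the plan's own assumptions imply that it narrows it. Part of the 5.2% is the Wald noninferiority test running at 2.8% rather than 2.5%, which no linking rule alters.

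**4. Split results away from the planned rates (illustrative).**

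| Weight-based under | Weight-based over | Safety won, noninferiority not met |
|---|---|---|
| 12% | 10% | 29% |
| 15% | 10% | 60% |
| 18% | 10% | 83% |
| 21.6% (margin) | 10% | 93% |
| 21.6% | 3.6% | 97% |
| 21.6% | 13.4% | 80% |
| 21.6% | 20% | 30% |

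In every row over-anticoagulation is truly below 27.8%, so the safety win is a correct rejection. At the margin, failing noninferiority is also the right answer. At 12% to 18% under, the true deficit (2.4 to 8.4 points) is inside the margin and the failure is lost power. No row contains a false primary claim.

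**5. Cost of a linking rule.**
- Noninferiority first: confirmatory safety power falls from 96.0% to 86.4%; noninferiority stays at 90.2%; the worst-case error falls from 5.2% to 2.8%.
- Both must win: 86.4%.
- Splitting alpha (two-sided 0.025 each): 150 per group for noninferiority and 118 for safety, against 127 and 100.

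**The case for a change.** The best case for a change is that the endpoints are mechanically linked and the document calls both tails harmful, so a gain in one is hard to interpret without the other. If weight-based dosing only shifted the fixed-dose distribution down without narrowing it, reaching 10% over would imply about 27% under. Safety would then be won in 96% of trials and noninferiority met in about 0.1%. A sentence costs no patients, and the choice of two separate claims ought to be stated.

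Some of this stands. The document is silent on a split result, and a stated reading would be clearer. But the shift example shows the noninferiority test doing its job: it fails almost every time, and that failure is itself a primary result. Nothing in the document allows it to be set aside, or says that one win is enough.

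The sentence is also not free. No section ranks effectiveness above safety, and the trial's title is about minimizing bleeding-related events. Making safety wait on effectiveness demotes the outcome nearest that title and takes its power below the 90% the plan states for it. Finally, the document is written in the past tense. If results were already known, an added gate would be post hoc and could neither confer nor remove confirmatory status. A rule in the cited methods publication cannot be excluded either.

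**Conclusion.** The concern does not call for a change. Followed as written, the plan gives two valid tests of two named questions, each correctly sized. The singular wording in Study Procedures refers to the measurement, and Study Outcomes makes clear that two outcomes come from it.

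The chance of any false favourable primary result is at most about 5.2%, reached only under an implausible joint null; elsewhere it is lower. The split result has a 9.6% chance at the planned rates and becomes common only where over-anticoagulation is truly reduced and under-anticoagulation truly increased. The two results then describe the trade-off accurately.

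What is missing is a rule for reading that case. A careful analyst fills it by reporting both primary results together and claiming no overall benefit of weight-based dosing when noninferiority is not met. This alters no estimate, interval or test. Whether to use a fixed sequence or a both-must-win rule is a design choice on which statisticians may differ, and here it would cost about 10 points of confirmatory safety power (96.0 − 86.4 = 9.6).

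These figures assume 127 evaluable per group, the planned fixed-dose rates, Wald-type tests and 0.05 as the alpha for safety. The rates in step 4 are illustrative.

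### Is the noninferiority conclusion left open because the plan never writes out the direction of the difference or the confidence limit that must clear -12%?

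*Combined protocol and SAP*

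**What the plan says.** All the relevant text is in the combined protocol and SAP.

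- **Arms** (Study Procedures): "Eligible patients were randomized to enoxaparin 40mg twice daily or enoxaparin 0.5mg/kg twice daily". Neither regimen is labelled test or reference.
- **Outcome** (Statistical Analysis): "The primary effectiveness outcome was avoidance of under-anticoagulation (peak aFXa <0.20 IU/mL"). A higher proportion is better.
- **Planning rates** (Statistical Analysis): a prior trial established that "90.4% of patients who received enoxaparin 40mg twice daily were not under-anticoagulated". For the other arm: "We assumed the rate of not being under-anticoagulated was 90.4% in the weight-based group".
- **Test** (Statistical Analysis): "The primary effectiveness analysis was a noninferiority analysis with a two-sided test at the 0.05 level". Then: "The noninferiority margin was set at -12" percent.
- **Interval**: a Poisson model with robust standard errors is fitted, followed by marginal estimation: "This method took the two estimated proportions used in the risk ratio, subtracted them, and computed the confidence interval for non-inferiority testing".
- **P-value**: "To obtain a two-sided noninferiority test p-value, we used a Wald post-test to compare the difference in proportions to the noninferiority margin constant -0.12".

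No sentence gives the order of subtraction, names the arm that must be noninferior, or identifies the limit that has to exceed -12%. Study Outcomes and Statistical Analysis refer to a published methods description for the outcome definitions and for the sample size calculations. That paper is not available here, so whether it states the rule cannot be checked.

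**The concern.** A noninferiority claim needs three things fixed in advance: the arm on trial, the direction of the difference, and the confidence limit compared with the margin. On a literal reading the document supplies none of them.

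The p-value adds a second worry. A two-sided test against -0.12 gives a small p-value when the difference is clearly better than the margin and also when it is clearly worse. Read without the interval or the estimate, it cannot separate noninferior from worse than the margin. If analysts were truly free to choose the direction or to rely on the p-value alone, the primary effectiveness conclusion could reverse on the same data.

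**Working it through.** **1. What the text fixes.**

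| Element | Source in Statistical Analysis | What it implies |
|---|---|---|
| Avoidance outcome, higher is better | Primary effectiveness outcome | Inferiority is a lower proportion in the test arm |
| Margin -12%, constant -0.12 | Margin and Wald test | With a favourable outcome, a negative margin means test minus reference, judged on the lower limit |
| 90.4% for 40 mg from a prior trial; 90.4% assumed for weight-based | Sample size inputs | 40 mg is the reference and weight-based the arm under test |
| 72.2% for 40 mg from a prior trial; 90% expected for weight-based | Primary safety outcome | The same roles in the other primary outcome |

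Everything points to weight-based minus fixed, lower limit above -12%.

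**2. The plan's own sample size.** Inputs: p = 0.904 in both arms, margin 0.12, power 90%.

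n per group = (z_alpha + z_power)² × 2p(1 − p) / margin²

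- 2 × 0.904 × 0.096 / 0.12² = 0.173568 / 0.0144 = 12.053.
- One-sided 0.025: (1.960 + 1.282)² × 12.053 = **126.65, so 127**. This is the stated figure.
- One-sided 0.05: (1.645 + 1.282)² × 12.053 gives 104.
- Two-sided equivalence: (1.960 + 1.645)² × 12.053 gives 157 at 0.025 per side; (1.645 + 1.645)² × 12.053 gives 131 at 0.05 per side.

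Among these variants, only a single limit of a two-sided 95% interval gives 127. With equal planning rates the calculation is symmetric, so it settles the sidedness but not the order of subtraction. The order comes from step 1.

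Power at 127: SE = √(0.173568 / 127) = 0.03697; 0.12 / 0.03697 − 1.960 = 1.286, which gives 90.1%. Exact binomial enumeration gives 0.902.

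**3. Do the interval and the p-value conflict?** Let d be weight-based minus fixed. If the estimate is above the margin, two-sided p < 0.05 means (d + 0.12)/SE > 1.960. Rearranged, this is d − 1.960 × SE > −0.12, which is the interval rule. Enumerating all 128 × 128 = 16,384 outcomes at 127 per group (unpooled Wald) gave 0 disagreements.

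**4. When is p small on the wrong side?** Take the fixed arm at 115/127 (90.6%), an illustrative count close to the planning rate.

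| Weight-based | d (points) | SE (points) | 95% CI (points) | (d + 0.12)/SE | Two-sided p |
|---|---|---|---|---|---|
| 110/127 | -3.9 | 3.98 | -11.7 to +3.9 | 2.02 | 0.043 |
| 109/127 | -4.7 | 4.04 | -12.6 to +3.2 | 1.80 | 0.072 |
| 87/127 | -22.0 | 4.87 | -31.6 to -12.5 | -2.06 | 0.039 |

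The first and last rows have similar p-values and opposite meanings, but the estimate and interval show at once which is which. A misleading p-value needs a shortfall of about 22 points. Enumerated at 90.4% in both arms, a significant result below the margin has probability 7.7 × 10⁻⁸.

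**The case for a change.** The strongest reply is that a primary success criterion should be stated, not reconstructed from sample size inputs, because the order of subtraction can decide the result. With 105/127 weight-based and 115/127 fixed, weight-based minus fixed is -7.9 points (CI -16.2 to +0.4, p = 0.33 against -0.12), so noninferiority is not shown. Subtracted the other way, the difference is +7.9 and p is about 0.000003, a clear pass. The methods paper is cited for outcome definitions and sample size, not expressly for the decision rule.

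What stands is the literal omission, and that stating the rule is better practice. The reversal does not stand as a risk of this plan. It would mean asking whether the 40 mg regimen is noninferior to weight-based dosing, and the planning text for both primary outcomes treats 40 mg as the comparator. The example shows what turning any noninferiority test around does.

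The p-value argument has the same limit. Nowhere does the plan say that p < 0.05 alone establishes noninferiority, and it computes the interval expressly for that purpose.

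**Conclusion.** No change follows. This is a gap in wording that an analyst fills in the only sensible way: weight-based minus fixed, noninferior if the lower limit of the two-sided 95% interval exceeds -12%, with the p-value read beside that interval. Applied so, the plan gives a sound conclusion. The 127 per group and the 90% power reproduce, and the two decision rules never disagree.

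One sentence stating the rule would be a courtesy to the reader. It would record what the analysts would do anyway. Because the section describes its analyses in the past tense, the sentence could not serve as prespecification either.

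Assumptions: the checks use an unpooled Wald interval at 127 per group as a stand-in for the robust Poisson marginal difference, with treatment as the only term and the same standard error for interval and test. A small-sample factor of N/(N − 1) on the robust variance (254/253 here) moves the limits by at most about 0.1 point and alters no conclusion in the examples. The observed counts are illustrative. What the methods paper says is unknown, but the conclusion does not depend on it.
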